### **7.10 Potential Benefits and Financial Compensation**

The treatment has the potential to provide benefit to the subject by reducing the effect of the underlying disease. In addition, this study will improve understanding of the safety and potential efficacy effects of administering IV adrabetadex in subjects with NPC1.

No financial compensation will be offered to subjects, guardians, or families. Travel, lodging, and per diem expenses may be covered per site policy.

### **7.11 Conflicts of Interest**

NIH ([name]) has been awarded US Patent 8,497,122, entitled "Biomarkers for Niemann-Pick C Disease and Related Disorders," for use of oxysterols as biomarkers for Niemann-Pick C disease. NIH (Dr.

[name]) has filed patent applications for use of protein biomarkers in NPC1. [name] has filed a patent application for the use of bile acid biomarkers in NPC1. Additional patent applications may be filed by institutions involved in this study that relate to the treatment or monitoring of therapy for NPC1.

[name] and NICHD have a Cooperative Research Agreement with Mandos, LLC for the development of intrathecal adrabetadex. [name] is an associate investigator on a Rush University protocol that supports expanded access for adrabetadex.

Mandos, LLC will provide adrabetadex. Mandos, LLC. may provide additional support to facilitate completion of this study. Mandos, LLC may use data obtained from this study to develop adrabetadex as a commercial product.

Collaborating or associate investigators may have funding or consulting relationships with pharmaceutical companies developing therapies for NPC1. Although these collaborating or associate investigators provide invaluable input, they are not directly responsible for the recruitment or enrollment of subjects into the Phase 1/2a protocol at the Washington University

## **8 Potential Risks and Discomforts**

Individual procedures and associated personal risks are briefly described, below.

### **8.1 Medical Evaluations**

There are no significant risks associated with the physical, neurological, and neuropsychiatric examinations. Multiple independent evaluations may be stressful to an infant. Clinical photographs or video may be obtained and these could potentially be embarrassing to some subjects.

### **8.2. Risk of Intravenous Adrabetadex**

The risks of intravenous adrabetadex are not known. Animal studies and human experience with HPBCD and adrabetadex to date suggest that intravenous administration of adrabetadex is generally safe and well-tolerated; however, a major purpose of this study is to further evaluate the safety and tolerability of intravenous adrabetadex in NPC1 subjects, as well as dose-response as assessed by reduction in plasma biomarkers and reduction in serum transaminases and liver size.

IV administration of an experimental drug could have untoward consequences including permanent disability or death.

Known toxic effects from the cat disease model include acute respiratory distress and death, and apparent irreversible deafness:

- Cats receiving 8,000 mg/kg HPBCD by subcutaneous injection developed acute respiratory distress and died due to this complication.
- Cats receiving multiple subcutaneous doses of 4,000 mg/kg or a single subcutaneous dose of 8,000 mg/kg HPBCD developed apparent irreversible deafness (36).
- A majority of mice receiving a single 8000 mg/kg subcutaneous dose of HPBCD had hearing loss due to loss of outer hair cells (37). However, chronic dosing at 4000 mg/kg showed an initial hearing loss that subsequently recovered suggesting that homeostatic mechanisms could adjust to the lower dosing.
- Pulmonary toxicity has been reported in young pigs receiving IV HPBCD infusions (38). Infusion of 1 g/kg of 40% HPBCD in normal saline over 40 minutes resulted in cardiovascular instability. Five infusions over two weeks of 0.25-0.5 g/kg over 40 minutes resulted in inflammatory pulmonary changes.

No adverse events related to pulmonary function have been reported for the children receiving IV or IT HPBCD under individual use INDs cited in the initial IND. The investigators are not aware of any pulmonary adverse events being reported in the eight other individuals receiving IV HPBCD under expanded access INDs in the United States. Those individuals are typically receiving 2500 mg/kg HP- $\beta$ -CD every week. Individuals in the US are receiving Kleptose HPB, from which adrabetadex is derived. Matsuo et al (33) reported in one subject transient diffuse pulmonary infiltrates and fever following infusions of IV HPBCD, which occurred after 23 months of therapy and in the context of recovery from an aspiration pneumonia. These resolved with prednisolone and antihistamine pretreatment and interpreted by the authors as a drug-related immunological reaction. The adverse pulmonary event appears to be related to high peripheral dosing. The HPBCD used by Matsuo et al is not the same preparation as adrabetadex.

While an allergic or anaphylactic reaction to adrabetadex is unlikely, the drug administration will take place in the Neonatal Intensive Care Unit, the Pediatric Intensive Care Unit, or the Infusion Center at St. Louis Children's Hospital, which provide close monitoring for acute adverse effects such as anaphylactic response to adrabetadex. Nursing and medical staff are trained in Code Blue procedures as well as Advanced Life Support, and many staff members are trained in Pediatric Advanced Life Support. Emergency resuscitation carts (Code Carts) are in place on every Patient Care Unit.

Exact doses for emergency resuscitation drugs for pediatric subjects (defined as less than 18 years of age) who weigh less than 50 kg are calculated immediately upon each admission and recorded on the Pediatric Emergency

Drug Sheet (PEDS). These include medications necessary for managing anaphylactic reactions (epinephrine, diphenhydramine and hydrocortisone). A copy of this document is kept on the subject's medical record as well as on the Code Cart on the Patient Care Unit for the duration of the admission. Code teams include a pediatrician.

### **8.3 Phlebotomy**

Phlebotomy is a risk/discomfort of this study. An anesthetic cream such as EMLA is an option to reduce discomfort. Infection and bruising are possible at the site of the blood draw. At each time point the maximum blood draw is 6 mL. In Phase 1, the maximum blood draw over 6 weeks is 24mL. In Phase 2, the maximum blood draw over 6 months will be 24mL. Nursing staff will monitor blood-drawing volumes. If blood limits are an issue, testing will be prioritized by the investigators. Safety laboratory tests will take priority over investigational testing. Not obtaining a test due to blood limit prioritization will not be considered a protocol deviation.

### **8.4 Audiological Evaluation**

Otoacoustic emissions (OAE) monitors for ototoxicity. OAE test is used to find out how well the inner ear, or cochlea, works. OAEs are sounds given off by the inner ear when responding to a sound. While the infant or child is sleeping, a small earphone, or probe is placed in the ear. The probe puts sounds in the ear and measures the sounds that come back.

### **8.5 Sedation**

Sedation for study procedures may be performed at the discretion of the research team in consultation with the guardians and anesthesiology. The medical and anesthesia clearance may determine that the subject is not fit for sedation during study procedures due to pre-existing medical conditions that would cause this elective procedure to be more risky. If that is the case, and sedation is necessary, the subject would be excluded from the study. If during the procedure complications of sedation arise or the level of sedation is inadequate, the procedure will be terminated.

The major risk associated with sedation is respiratory collapse. In order to minimize this possible complication, sedation will be performed by experienced pediatric physicians. Facilities for maintenance of a subject's airway, artificial ventilation, and circulatory resuscitation will be immediately available and ready for use. The anesthesiologist will also select the anesthetic agent used based on their clinical judgment. Another risk of sedation is aspiration. Intubation decreases the risk of aspiration and may be used if in the opinion of the anesthesiologist that it is indicated. Death is a rare complication of sedation when performed by a licensed anesthesiologist under controlled conditions.

### **8.6 Chest X-ray**

A chest X-ray (CXR) will be obtained on the first admission to check placement of a peripherally inserted central catheter or other central IV line for drug administration, and this will serve as a baseline study should pulmonary symptoms be observed during the study.

There is no discomfort and minimal exposure to radiation with a CXR. X-rays usually have no side effects in the diagnostic range. The CXR is one of the lowest radiation exposure medical examinations performed today. The effective radiation dose from this procedure is about 0.8 mSv, which is about the same as the average person receives from background radiation in 10 days. Female participants should always inform any study coordinators, nurses and the x-ray technologist if there is any possibility that they are pregnant. The amount of radiation the subject will receive in this study is up to 0.04 rem, which is below the guideline of 5 rem per year allowed for research subjects by the NIH Radiation Safety Committee. The average person in the US receives a radiation exposure of 0.3 rem per year from natural sources, such as the sun, cosmic radiation, and the earth's air and soil. If the subject/guardian would like more information about radiation, he/she will ask the investigator for a copy of the pamphlet, An Introduction to Radiation for NIH Research Subjects.

While there is no direct evidence that the amount of exposure received from participating in this study is harmful, there is indirect evidence it may not be completely safe. There may be a very slight increase in the risk of cancer. The subject/guardian will inform one of the doctors if he/she has had any radiation exposure in the past year, either from other research studies or from medical tests or care, so the doctors can make sure that the subject will not receive too much radiation. Radiation exposure includes x-rays taken in radiology departments, cardiac catheterization, and fluoroscopy as well as nuclear medicine scans in which radioactive materials were injected into the subject's body. If the subject is pregnant or breast feeding, she may not participate in this research study. It is best to avoid radiation exposure to unborn or nursing children since they are more sensitive to radiation than adults.

## **8.7 Liver/Spleen Ultrasound**

The risks of an abdominal ultrasound are limited to mild discomfort of the technicians pressing the probe against the abdominal wall.

## **8.8 Peripherally Inserted Venous Catheter (PICC) and Risks**

Insertion of a peripherally inserted venous catheter (PICC line) or other central IV line may be required for administration of the adrabetadex drug in this study due to the limited peripheral IV access in the neonatal patients, the dosing frequency, and the number of doses. The preferred central IV line of choice is a PICC line. In situations where a PICC of insufficient gauge to support the IV infusion and compliance with protocol activities, or where an indwelling central line is otherwise medically indicated, alternative central IV lines, such as a Broviac, can be used for drug delivery. In the open label extension, the increased age of the patients and reduced dosing frequency will permit administration of the drug via peripheral IV access. Study procedures will be performed at a high-volume center with a dedicated pediatric service. At the time of subject consent, there will be discussion with the parents or guardian regarding the nontherapeutic nature of the PICC line procedure and the requirement for procedural sedation. A centrally placed, venous catheter is required for administration of adrabetadex. For this study, we expect to utilize a PICC line. The PICC line will be placed by a qualified and experienced person. In the neonatal population, insertion of a PICC line is normally accompanied by sedation and will not be withheld to avoid its risks. Rare risks associated with this procedure include bleeding at the site of insertion, thrombosis on or in the catheter, and systemic infection.

## 9. Study Procedures and Schedule

### 9.1 Overview of Study

Subjects who have been screened for eligibility will be admitted to the Neonatal Intensive Care Unit or the Pediatric Intensive Care Unit depending on age for inpatient baseline qualification assessments after written informed consent has been obtained. In phase 1 of the study, the first admission will last approximately 7 days. Subjects may then be followed as outpatients for the subsequent five weeks, or they may remain inpatient if clinically indicated. Upon initiation of the study, a PICC line or other intravenous access will be placed and baseline laboratory testing and liver/spleen ultrasound will be obtained. Drug will be administered twice a week with an interval of  $4 \pm 1$  days. A total of 12 doses will be given. Subjects who demonstrate significant reduction either in the glycine-conjugated trihydroxycholanic acid biomarker or serum bilirubin (direct bilirubin or direct bilirubin:total bilirubin ratio) will be allowed to crossover into the second phase of the study, an open-label phase of six months duration. In this phase of the study, dosing frequency will be monthly with IV adrabetadex for six months for a total of six administrations. Subjects will be evaluated at each study visit for evidence of adverse effects.

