### **3. Study Objectives**

The overall goal of this study is to reduce the risk of progressive hepatic fibrosis due to inflammation in infants with Niemann-Pick Disease, type C. The objectives of this study are to determine the safety, tolerability and efficacy of intravenous adrabetadex in NPC disease following 12 doses given twice weekly for 6 weeks. The primary endpoint is the efficacy of adrabetadex to reduce plasma levels of glycine-conjugated trihydroxycholanic acid ("bile acid biomarker"), an NPC-specific pharmacodynamic biomarker. Secondary endpoints are assessment of the dose-response relationship for attenuation of liver dysfunction, as determined by reduction in serum transaminases (ALT and AST) and liver size. Exploratory lipid, protein and inflammatory biomarkers will also be examined. Subjects who demonstrate significant reduction either in the glycine-conjugated trihydroxycholanic acid biomarker or serum bilirubin (direct bilirubin or direct bilirubin:total bilirubin ratio) will be allowed to crossover into the second phase of the study, an open-label phase of six months duration in which IV adrabetadex will be administered monthly for a total of six doses. Serum transaminases (ALT and AST) and an abdominal ultrasound will be obtained at the end of the six-month open-label extension phase. Efficacy will be assessed by reduction in serum transaminases and reduction in spleen volumes. NPC biomarkers (cholestane-3 $\beta$ ,5 $\alpha$ ,6 $\beta$ -triol, glycine-conjugated trihydroxycholanic acid,PPCS/lipid-509, 24(S)-hydroxycholesterol, 27-hydroxycholesterol, and neurofilament light chain) will also be obtained at these time points and will be considered exploratory outcome measures.

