## 5. Study Design and Methods

### 5.1 Study Overview

The trial will be a Phase 1/2a, open-label, dose-escalation, multi-center study of adrabetadex in subjects with NPC dosed twice a week with IV adrabetadex for six weeks for a total of 12 administrations, followed by a six month open-label extension phase in which the subjects are dosed monthly with IV adrabetadex for six months for a total of six administrations. The study will characterize the safety, tolerability, preliminary efficacy, and pharmacodynamics of IV adrabetadex. The primary outcome will be the efficacy of adrabetadex to reduce plasma levels of an NPC bile acid biomarker, a cholesterol-derived NPC1 disease-specific biomarker that serves as a pharmacodynamic (PD) measure of the effect of the drug to reduce the oxidizable cholesterol pool in liver tissue. The secondary outcome measure will be the examination of the dose-response relationship for attenuation of liver dysfunction, as determined by reduction in serum transaminases (ALT and AST) and liver size. This study will also evaluate the effect of intravenous adrabetadex on a series of disease-associated serum biomarkers.

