## **6.7 Research Laboratory Testing**

Plasma and serum will be collected for biomarker analysis. Sample collection, processing and storage will be standardized. Coded samples will be sent to NICHD Biorepository for long-term storage. Testing may be performed in clinical or research laboratories. Research testing will include, but is not limited to the following:

Markers of cholesterol homeostasis (phase 1: Baseline, 2, 4 and 6 weeks; 0.5 ml/time point; 2 mls total over 6 weeks; phase 2: Baseline, 2, 4 and 6 months; 0.5 ml/time point; 2 mls total over 6 months)

1. Trihydroxycholanic acid glycine conjugate (bile acid biomarker)
2. Cholestan-3 $\beta$ ,5 $\alpha$ ,6 $\beta$ -triol
3. PPCS/Lipid-509

Plasma lipidomics (phase 1: Baseline and 6 weeks; 0.5 ml/time point; 1 ml total over 6 weeks; phase 2: 6 months; 0.5 ml/time point; 0.5 ml total over 6 months)

1. Sphingolipids: sphingoid bases, ceramides, glucosylceramides, lactosylceramides, gangliosides
2. Lysosphingolipids: lyso-sphingomyelin

Additional biomarkers for NPC (phase 1: Baseline, 2, 4, and 6 weeks; 1.75ml/time point; 7mls over 6 weeks; phase 2: Baseline, 2, 4, and 6 months; 1.75 ml/time point; 7 mls total over 6 months)

- Serum 24(S)-hydroxycholesterol
- Serum 27-hydroxycholesterol
- Serum neurofilament light chain

Lab results do not need to be resulted and reported prior to dosing.

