### 9.2 Outline of Protocol Admissions and Testing

Time	Major Events	Admission Type	Length
Phase 1			
Week 1	Enrollment and consent PICC/IV line placement Liver/spleen ultrasound Obtain baseline laboratory testing Administration of 1 st and 2 nd dose	Inpatient	7 days
Weeks 2-6			
Weeks 2-6	Administration of doses 3-12 Obtain laboratory testing	Outpatient*	10 days
Week 6	Liver/Spleen ultrasound PICC line removal	Outpatient*	1 day
Week 7	Post-dose safety evaluation	Outpatient*	1 day
Phase 2			
Month 1	Initiation of open-label extension one month $\pm 7$ days month after dose 12 Obtain baseline laboratory testing Administration of dose 13	Outpatient*	1 day
Months 2-6	Administration of doses 14-18 Obtain laboratory testing	Outpatient*	1 day
Month 6	Liver/Spleen ultrasound Post-dose safety evaluation	Outpatient*	1 day

\*May be performed as inpatient if the patient remains hospitalized

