### **9.6 Doses 3-12**

These drug administrations may occur as an outpatient. Interval between dosing will be  $4 \pm 1$  days.

IV adrabetadex will be administered IV at a rate of 250 mg/kg/hr. Rate may be decreased in 25 mg/kg/hr increments to 175 mg/kg/hr if required. The rate and reason for reduction will be recorded.

Vital signs (temperature, heart rate, respiratory rate, supine blood pressure, and  $\text{SaO}_2$ ) and standard neurological checks will be conducted at least every 30 minutes during and then for the two hours after drug administration. Subject may be discharged 2 hours post administration if no issues.

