### **9.7 Phase 1: Final Evaluation**

The final evaluation will occur  $2 \pm 1$  days after the 12th adrabetadex infusion. This will include a liver/spleen ultrasound. PICC line will be removed.

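### The nominal 4-day dosing interval conflicts with 12 doses in six weeks, and the week-6 blood sample for the primary biomarker is not tied to dose 12

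*Combined protocol and SAP*

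**What the plan says.** **Frequency and duration.** Section 5.1 describes subjects "dosed twice a week with IV adrabetadex for six weeks for a total of 12 administrations". Section 5.6 repeats this, and section 9.1 adds "A total of 12 doses will be given". The objective in section 3 is the effect "following 12 doses given twice weekly for 6 weeks".

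**Interval.** Section 9.1: "Drug will be administered twice a week with an interval of" 4 ± 1 days. Section 9.6: "Interval between dosing will be" 4 ± 1 days.

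**Calendar.** The outline in section 9.2 puts doses 1 and 2 in week 1. Its row for weeks 2-6 reads "Administration of doses 3-12 Obtain laboratory testing". Ultrasound and PICC removal are in week 6 and the safety evaluation in week 7. Section 5.3 gives Phase 1 seven weeks in all.

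**Blood samples.** Section 6.7: "Markers of cholesterol homeostasis (phase 1: Baseline, 2, 4 and 6 weeks; 0.5 ml/time point". Sections 6.3 (AST and ALT) and 6.6.1 (which includes bilirubin) use the same four times. None gives a window or a dose number. Section 10 names the plasma bile acid biomarker as primary but fixes no analysis time.

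**Visits tied to dose 12.** The final evaluation (section 9.7) is 2 ± 1 days after it: "This will include a liver/spleen ultrasound. PICC line will be removed". No blood draw is listed. The safety contact (section 9.8), at 7 ± 2 days, is by history and may be by telephone.

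**The concern.** Two gaps meet at the primary endpoint. First, a site that doses at the stated nominal interval cannot also keep to the week table. Second, the biomarker sample is timed by the calendar, whereas the objective is defined by the number of doses. If dosing runs late and the sample does not move with it, the primary measurement is taken before the course is complete.

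Both the number of doses received and the time since the last infusion could then differ between infants. The biomarker is a pharmacodynamic marker, there are six infants per cohort, and section 10 bases its power statement on five. The biomarker and bilirubin also decide entry to Phase 2 (sections 9.1 and 9.9), so the timing of the same draw may bear on individual eligibility.

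**Working it through.** **Inputs.** 12 doses, hence 11 intervals (sections 5.1, 5.6, 9.1). Interval 3 to 5 days, nominal 4 (sections 9.1, 9.6). Final evaluation 1 to 3 days after dose 12 (section 9.7). Safety contact 5 to 9 days after dose 12 (section 9.8). Dose 1 is set on day 1, so week 6 is days 36-42 and seven weeks end on day 49.

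**The plan's own figure.** 2 doses a week × 6 weeks = 12 doses, which reproduces the plan. The mean interval this needs is 7/2 = 3.5 days, and 1 + 11 × 3.5 = 39.5, inside six weeks.

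**Formulas.** For a constant interval d, day of dose 12 = 1 + 11d, and doses by day 42 = min(12, floor(41/d) + 1). Alternating gaps starting with 3 days sum to 6 × 3 + 5 × 4 = 38; starting with 4 days they sum to 6 × 4 + 5 × 3 = 39.

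| Gaps | Dose 12 | Final evaluation | Safety contact | Doses by day 42 |
|---|---|---|---|---|
| every 3 days | day 34 | 35-37 | 39-43 | 12 |
| alternating 3, 4 | day 39 | 40-42 | 44-48 | 12 |
| alternating 4, 3 | day 40 | 41-43 | 45-49 | 12 |
| every 4 days (nominal) | day 45 | 46-48 | 50-54 | 11 |
| every 5 days | day 56 | 57-59 | 61-65 | 9 |

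The rows for 3 and 5 days satisfy the interval rule only. They amount to 7/3 = 2.3 and 7/5 = 1.4 doses a week.

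**All schedules in the window.** Whole-day gaps of 3, 4 or 5 days give 3^11 = 177,147 schedules. Of these, 31,824 (18%) finish by day 42, and 14,278 of those also place exactly two doses in each calendar week. These are counts of what the text permits, not probabilities.

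**Doses before a week-6 sample.** If two doses fall in every week, doses 11 and 12 fall in week 6. A sample on some day of that week can then follow 10, 11 or 12 doses. At the nominal interval, dose 11 is on day 41 and dose 12 on day 45, so a day-42 sample follows 11 doses.

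**Time since the last infusion, day-42 sample.** Every 3 days: 42 − 34 = 8 days. Alternating: 42 − 39 = 3 or 42 − 40 = 2 days. Every 4 days: 42 − 41 = 1 day.

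**The case against.** The strongest reply is that twice a week and 4 ± 1 days stand in one sentence and both bind. An ordinary alternating 3- and 4-day pattern meets both, fits the week table, and brings the safety contact in by day 49. On this reading the nominal 4 is a rounded 3.5. That stands as far as it goes: a reader might infer that no schedule in the window gives 12 doses in six weeks, and this is wrong. It does not remove the conflict for a site that follows the stated nominal figure.

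A reader might also infer that the sample could follow as few as 9 doses, which is 3/12 = 25% less exposure. That needs 5-day gaps throughout, which break the twice-weekly rule and the week table. It illustrates the conflict and does not describe compliant conduct. Nor do the documents support a systematic difference between cohorts, because both follow the same interval and sampling rules.

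On the sample, one can say that week 6 already means the dose-12 visit. Section 6.4 sets the ultrasound at 6 weeks, and section 9.7 performs it 2 ± 1 days after dose 12. The list in section 9.7 is also not exhaustive: it omits the audiology that section 6.5 requires at the end of Phase 1, and section 9.6 omits the week-2 and week-4 bloods. This is a fair reading of intent, but no section says it of the bloods. The outline table places laboratory testing in the weeks 2-6 row and not in the week-6 row with the ultrasound.

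**Conclusion.** The point holds in two parts. The nominal 4-day interval conflicts with twice-weekly dosing for six weeks, with the week table and with the seven-week Phase 1: dose 12 falls on day 45 and the safety contact no earlier than day 50. Taken alone, the window allows dose 12 anywhere from day 34 to day 56, although compliant schedules exist within it. Separately, nothing in the text guarantees that the end-of-Phase-1 biomarker, AST/ALT and bilirubin samples follow dose 12, even at a fully compliant site. A week-6 sample follows 10 to 12 doses if all rules bind, or 11 on day 42 at the nominal interval, with a varying time since the last infusion.

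This rests on dose 1 being on day 1, and on the week-6 sample being the one used for the primary analysis, which section 10 does not state. That the same sample decides Phase 2 entry is likewise an inference. The documents give no data on how the biomarker changes between doses 10 and 12 or with days since infusion, so the added variability cannot be quantified. The trial can run as planned, but this should be corrected, because the primary measurement is not fixed in relation to treatment.

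**What to change.** List the already planned end-of-Phase-1 blood draw (primary biomarker, AST/ALT, bilirubin) in section 9.7, at 2 ± 1 days after dose 12. Define that draw as the week-6 sample in sections 6.3, 6.6, 6.7 and 10, and name it in section 10 as the primary analysis time point if that is the intent. Record for each infant the number of doses received and the days since the last infusion.

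The sponsor must also reconcile the frequency, interval and calendar statements in sections 5.1, 5.6, 9.1, 9.2 (outline) and 9.6. Which schedule stands is the sponsor's decision.

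The cost is amendment wording. The visit exists and no blood volume is added. For some infants the draw falls a few days later: at the nominal interval on days 46-48, which is 4 to 6 days after day 42. Phase 2 starts one month ± 7 days after dose 12. Taking a month as 30 days, at least 30 − 7 − 3 = 20 days remain between the draw and dose 13 for the result to inform entry.
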